12.2.2. Dose Reduction for Decreased Glomerular Filtration Rate (GFR)

Selinexor is not significantly eliminated by the kidney. Therefore, no dose alteration of selinexor/placebo is required in patients with renal dysfunction.

12.2.3. Dose Adjustment in the Setting of Infection

Patients with active uncontrolled or suspected infections should have treatment interrupted until the patient is clinically stable. When ready to resume dosing, treatment may continue at the original dose. Missed doses will not be replaced. Patients may continue antibiotics for prolonged periods while re-initiating their treatment at the discretion of the Investigator.

12.2.4. Conditions Not Requiring Dose Reduction

The following conditions are exceptions to the guidelines. Dosing does not need to be interrupted in the following cases:

- Alopecia of any grade
- Electrolyte or serum analyte (eg, urate) abnormalities that is reversible with standard interventions
- Isolated values of Grade ≥ 3 alkaline phosphatase. Determination of liver versus bone etiology should be made, and evaluation of gamma-glutamyl transferase, 5' nucleotidase, or other liver enzymes should be performed.

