For all \geq Grade 3 hematological or Grade 3 non-hematological AEs that are NOT treatment related, after consultation with the Medical Monitor and at the discretion of the Investigator, dosing may be maintained provided that the patient can continue to take the agent by mouth.

For all Grade 4 non-hematologic toxicities, protocol-specified study treatment (selinexor/placebo) must be suspended and the Sponsor Medical Monitor consulted regarding options for continuation (ie requirements for resuming study treatment or permanent discontinuation).

Table 8: Pre-specified Dose/Schedule Modifications for Adverse Events Related to Selinexor/Placebo Treatment

| Dose Level¹ | Dose/Schedule Modifications of Selinexor/Placebo² | |
|---------------------------------|---|--|
| | Total mg Selinexor/Placebo Per Week | Selinexor/Placebo Dose/Schedule |
| Dose level 0 (starting dose) | 120 mg | 60 mg selinexor/placebo (3 tablets) twice weekly (Day 1, Day 3) |
| Dose level -1 | 100 mg | 100 mg selinexor/placebo on Day 1 OR divided as 60 mg selinexor/placebo on Day 1 and 40 mg selinexor/placebo on Day 3 |
| Dose level -2 | 80 mg | 80 mg selinexor/placebo on Day 1 OR 40 mg selinexor/placebo on Days 1 and 3 |
| Dose level -3 | 60 mg | 60 mg selinexor/placebo on Day 1 OR divided as 40 mg selinexor/placebo on Day 1 and 20 mg selinexor/placebo on Day 3 |
| Dose level -4 | 40 mg | 40 mg selinexor/placebo on Day 1 OR 20 mg selinexor/placebo on Days 1 and 3 |

¹For some AEs, dose interruption rather than reduction is recommended. See [Table 9](#) for specific recommendations.

²All placebo doses will contain 0 mg of selinexor.

Table 9: Supportive Care and Dose Adjustment Guidelines for Selected Adverse Events

| Toxicity and Intensity | Supportive Care and Dose Adjustment Guidelines |
|--|---|
| Fatigue | |
| Grade 1 | 
Maintain dose. Rule out other causes. If found to be anemic and symptomatic, consider transfusing even with hemoglobin >8 g/dL (anemia Grade <3).
 
Patients with significant fatigue after several doses of selinexor may have an antitumor response. Consider an unscheduled assessment of tumor response as part of the patient's evaluation.
 |
| Grade 2 lasting ≤7 days | 
As per NCCN guidelines, consider stimulants such as methylphenidate 5mg QD in the morning only.
 |

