| Grade 3 | 
Rule out other causes. Use additional anti-nausea medications to supplement the protocol-required 5-HT3 antagonist(s). Olanzapine 2.5 to 5 mg PO every morning, as per NCCN guidelines, can mitigate nausea and anorexia.
 
Interrupt selinexor dosing until resolved to Grade ≤ 2 or baseline and reduce selinexor by 1 dose level.
 
Patients with significant nausea/vomiting after several doses of selinexor may have an antitumor response. Consider an unscheduled assessment of tumor response as part of the patient's evaluation.
 |
| Hyponatremia | |
| Grade 1 (sodium levels < Normal to 130 mmol/L) | 
Maintain dose. Rule out other causes including drug (eg, diuretic) effects.
 
Be certain that reported sodium level is corrected for concurrent hyperglycemia (serum glucose > 150 mg/dL).
 
Treat hyponatremia per institutional guidelines including dietary review. Provide supplemental oral and/or intravenous fluids if dehydration is present. Consider addition of salt tablets to patient's diet.
 |
| Grade 3 with sodium levels <130-120 mmol/L without symptoms | 
Rule out other causes including drug (eg, diuretic) effects.
 
Be certain that reported sodium level is corrected for concurrent hyperglycemia (serum glucose > 150 mg/dL).
 
If (corrected) sodium is Grade ≤ 3 and continues to be asymptomatic, then patient may continue current dosing without interruption provided that IV saline and/or salt tablets are provided and patient is followed closely.
 
If Grade 3 is persistent or worsens or does not respond to treatment, interrupt selinexor dosing until resolved to Grade 1 or baseline and reduce selinexor by 1 dose level.
 |
| Grade 3 with sodium levels <130-120 mmol/L with symptoms or Grade 4 (<120 mmol/L) | 
Rule out other causes including drug (eg, diuretic) effects.
 
Be certain that reported sodium level is corrected for concurrent hyperglycemia (serum glucose > 150 mg/dL).
 
Interrupt selinexor dosing until resolved to Grade 1 or baseline and without symptoms. Reduce selinexor by 1 dose level.
 |
| Diarrhea | |
| Grade 1 | 
Maintain dose. Rule out other causes including drug effects. Treat per institutional guidelines with anti-diarrheals, such as loperamide.
 |

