| Grade ≥ 3 with bleeding | 
Interrupt selinexor dosing and check platelet counts weekly until the bleeding has stopped, patient is clinically stable and the platelets have recovered to Grade 2 or baseline. When resuming selinexor, reduce by 1 dose level.
 
If recurrent, unless contraindicated, initiate treatment with moderate to high doses of thrombopoietin stimulating agents as above.
 |
| Neutropenia | |
| Grade 3 or 4 neutropenia (afebrile) OR Febrile neutropenia | 
Institute colony stimulating factors and prophylactic antibiotics as clinically indicated per institutional guidelines.
 
Interrupt selinexor and check neutrophils at least weekly until recovers to Grade 2 or baseline and without fever (if febrile) and the patient is clinically stable. Reinitiate selinexor therapy and colony stimulating factors per institutional guidelines.
 
If recurrent, continue colony stimulating factors, interrupt selinexor until neutrophil counts improve to Grade ≤ 2 or baseline levels, and reduce dose of selinexor 1 dose level.
 |
| Anemia | |
| Treat per institutional guidelines including blood transfusions and/or erythropoietins. Consider transfusing for symptoms with hemoglobin > 8 g/dL (Grade < 3) or for any Grade 3 (hemoglobin < 8 g/dL). If possible, maintain selinexor dose as long as patient is clinically stable, but if a dose reduction or interruption is desired, consult with the Medical Monitor. | |

| Toxicity and Intensity | Supportive Care and Dose Adjustment Guidelines |
|--|---|
| Tumor lysis syndrome | |
| If TLS risk factors are identified, provide prophylactic IV hydration and regular monitoring of hydration (especially when increasing the dose of selinexor), renal function, urine output, and clinical laboratory measures of interest for TLS (eg, phosphorus, potassium, calcium, LDH, uric acid). Consider administration of hypouricemic agents to reduce the risk of TLS. | |
| Hold selinexor in patient with hyperkalemia (≥ 7.0 mmol/L) and/or symptoms of hyperkalemia, an increase in uric acid, or other changes in biochemical blood parameters suggestive of TLS. Start IV hydration, and consider hypouricemic agent until levels return to normal. Selinexor can be reintroduced at the normal or reduced dose. | |
| Other selinexor-related adverse events | |
| Grade 1 or 2 | Rule out other causes. Maintain dose. Start treatment and/or standard supportive care per institutional guidelines. |

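### Protocol Section 12.2.4 exempts reversible electrolyte and urate abnormalities from dose interruption without limit, in conflict with Table 9 for symptomatic Grade 3 or Grade 4 hyponatremia, with the Grade 4 rule in Section 12.2.1 and, read literally, with the tumor lysis row

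*Protocol*

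**What the plan says.** Protocol Section 12.2.4 (Conditions Not Requiring Dose Reduction) opens: "The following conditions are exceptions to the guidelines. Dosing does not need to be interrupted in the following cases". One of its three bullets is "Electrolyte or serum analyte (eg, urate) abnormalities that is reversible with standard interventions". The bullet carries no grade ceiling, no condition on symptoms and no mention of tumor lysis.

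Three other places in Section 12.2.1 cover some of the same events:

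- **Table 9, last hyponatremia row** (Grade 3 with symptoms, or Grade 4, meaning sodium below 120 mmol/L): "Interrupt selinexor dosing until resolved to Grade 1 or baseline and without symptoms. Reduce selinexor by 1 dose level". It makes no exception for cases that correct.
- **Text before Table 8:** "For all Grade 4 non-hematologic toxicities, protocol-specified study treatment (selinexor/placebo) must be suspended", with the Medical Monitor to be consulted on whether and how to continue.
- **Table 9, tumor lysis syndrome row:** selinexor is held for potassium of 7.0 mmol/L or more and/or "symptoms of hyperkalemia, an increase in uric acid, or other changes in biochemical blood parameters suggestive of TLS". Hydration and a hypouricemic agent are used until values normalise, after which drug may be reintroduced.

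**The concern.** Because Section 12.2.4 calls its list exceptions, a site can fairly take it as permission to keep dosing despite Table 9. For a correctable sodium, potassium or urate abnormality, that permission meets instructions elsewhere to interrupt, hold or suspend. No cross-reference or order of precedence settles it.

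Patient safety is the main stake. Protocol Section 5 lists hyponatremia among the most commonly reported treatment-related events in the Phase 1 sarcoma study (events there were primarily Grade 1 or 2), and SAP Table 5-1 makes it an adverse event of clinical interest. A secondary stake is interpretation: if handling depends on the site, the planned counts of dose interruptions and reductions (SAP Section 3.4.1), and of adverse events leading to them (SAP Section 5.1.3), partly reflect which section each site followed.

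**Working it through.** The check is a comparison of text. The only arithmetic is the dose difference.

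**Step 1. Apply each rule to the same event.** Every event is taken as correctable unless stated.

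| Event | Section 12.2.4 | Table 9 | Grade 4 rule, Section 12.2.1 | Result |
|---|---|---|---|---|
| Grade 1 hyponatremia | No interruption needed | Maintain dose | Not engaged | Consistent |
| Asymptomatic Grade 3 hyponatremia, responding | No interruption needed | May continue while treated | Not engaged | Consistent |
| Asymptomatic Grade 3 hyponatremia, not responding | Does not apply: not reversing | Interrupt and reduce | Not engaged | Consistent |
| Symptomatic Grade 3 hyponatremia | No interruption needed | Interrupt and reduce | Not engaged | Conflict |
| Grade 4 hyponatremia | No interruption needed | Interrupt and reduce | Suspend | Conflict with both |
| Potassium or uric acid change suggesting tumor lysis | No interruption needed | Hold | Depends on grade | Conflict on literal wording |
| Isolated uric acid rise, no suspicion of tumor lysis | No interruption needed | Can be read as outside the tumor lysis row | Depends on grade | No necessary conflict with that row |

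The second and third lines rest on the asymptomatic Grade 3 row, which already turns on reversibility: the "patient may continue current dosing without interruption provided that IV saline and/or salt tablets are provided and patient is followed closely", and "If Grade 3 is persistent or worsens or does not respond to treatment, interrupt selinexor dosing until resolved to Grade 1 or baseline".

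**Step 2. Look for a rule of precedence.** There is none. If Section 12.2.4 prevails, the Table 9 interruption is void for correctable symptomatic Grade 3 or Grade 4 hyponatremia, and the mandatory Grade 4 suspension is contradicted. If Table 9 prevails, the label of exception has no force for these events. Two features add to the doubt. Table 9 repeats the alkaline phosphatase exception in its row for other selinexor-related events but does not repeat the electrolyte and urate one. And the heading of Section 12.2.4 speaks of reduction while its text speaks of interruption.

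**Step 3. Dose at stake for hyponatremia** (Table 8). Level 0: 60 mg × 2 = 120 mg per week. Level -1: 100 mg per week. Under Section 12.2.4, 120 mg per week continues. Under the last hyponatremia row, the dose is 0 until recovery, then 100 mg per week. The lasting difference is 120 − 100 = 20 mg per week, or 20/120 = 16.7%, plus the doses omitted during the interruption. The tumor lysis row differs: it allows return at the normal or a reduced dose.

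**Step 4. When the question arises.** Section 10.6.2.1 puts sodium and potassium in both chemistry panels, so they are measured at all six Cycle 1 visits. Uric acid is in the complete panel only, scheduled for Day 1 of each cycle. The same section asks for results to be reviewed before dosing. Whether an abnormality is reversible may be known only after treatment, so a site applying Section 12.2.4 is making a forecast.

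**The case against.** Four points deserve weight.

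- **Permission against direction.** Section 12.2.4 says interruption is not needed; it does not forbid it. A site that follows Table 9 breaches nothing. This stands, and it means the rules are not two opposite commands. But permission labelled an exception still authorises dosing where other text requires stopping.
- **Grade 4 is the clearest case for stopping.** The suspension rule is mandatory and covers all such toxicities, and the notes to Table 9 base modifications on the worst preceding toxicity, so later correction does not erase the grade. Many sites would probably suspend. Still, the text offers them an unlimited exception and does not say that it yields.
- **A harmonising reading exists.** Section 12.2.4 could be taken as modifying only the Table 9 row for other selinexor-related events, where the alkaline phosphatase exception reappears, leaving hyponatremia and tumor lysis to their own rows. That is plausible, but the protocol does not say so.
- **The uric acid trigger sits in a tumor lysis row.** Its closing words suggest that the rise meant is one pointing to tumor lysis. Section 13.1.2.2.1 reports 8 such cases (about 0.3%), all in myeloma or other hematological malignancies. This stands, and the urate conflict is therefore claimed only on the literal wording.

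A reader might go further and infer that the exemption swallows most of the hyponatremia guidance. The documents do not support that: only the last row conflicts, and nothing in them says how often such cases correct. Nor do they support a conflict for every uric acid rise.

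**Conclusion.** The contradiction is real but narrow. It covers correctable symptomatic Grade 3 or Grade 4 hyponatremia, with Grade 4 also caught by the general suspension rule, and, on literal wording, potassium or uric acid changes in the tumor lysis row. Hyponatremia of Grade 1 and asymptomatic Grade 3 is handled consistently.

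For an affected hyponatremia case at the starting level, the choice is 120 mg per week uninterrupted, or none until recovery followed by 100 mg per week. How many patients this touches cannot be estimated, because the documents give no rate of severe events; Section 5 describes the common events as primarily Grade 1 or 2.

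The conclusion assumes that the exception label applies to the whole dose guidance, as its wording allows, and that no manual outside these documents supplies a precedence rule. A reader might also infer a threat to the trial's inference. There is none: the affected counts are descriptive, and alpha, power and the primary analysis are unchanged. The reason to act is patient safety and uniform conduct.

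**What to change.** The sponsor should reconcile four places: Section 12.2.4, the last hyponatremia row of Table 9, the tumor lysis row of Table 9, and the Grade 4 rule in the text of Section 12.2.1. It should state which prevails when more than one applies. Which events may continue and which must stop is for the sponsor to decide; no rule is proposed here.

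A clarification letter or an amendment would do. The cost is a few reworded lines and notice to sites, with no new procedures, data or analyses. It is worth doing even though the SAP reports enrollment as concluded, because Sections 7.2.3 and 12.1.3 provide for continued open-label selinexor.

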12.2.4.1. Missed or Vomited Doses

Missed and Delayed Doses

A maximum of 2 doses may be given per week.

If a dose was missed, the schedule of that week should be altered to accommodate two doses in that week with at least 36 hr between two consecutive doses.

If a dose must be skipped (eg, due to recommendation of Investigator), the next dose will be taken as per schedule. Doses should not be administered less than 36 hr apart and all missed and delayed doses should be documented.

Vomited Doses

If a dose is vomited within one hour of ingestion, it will be replaced. If vomiting occurs more than one hour after dosing, it will still be considered a complete dose.

If a patient missed a full week of dosing for non-study treatment related events (eg, a required medical procedure or an unanticipated personal emergency), the days missed will not be replaced. For example, if patient missed dosing from Cycle 2 Day 7 to Cycle 2 Day 14, then the patient will re-start dosing on Cycle 2 Day 15.

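### Read as written, the missed-dose rule doubles the Table 8 weekly total for a patient on a once-weekly reduced dose

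*Protocol*

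**What the plan says.** Protocol Section 12.2.4.1 opens with a cap: "A maximum of 2 doses may be given per week". For a missed dose, "the schedule of that week should be altered to accommodate two doses in that week with at least 36 hr between two consecutive doses". For a dose that has to be skipped the rule differs: "If a dose must be skipped (eg, due to recommendation of Investigator), the next dose will be taken as per schedule". A spacing limit follows: "Doses should not be administered less than 36 hr apart and all missed and delayed doses should be documented".

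Vomiting has its own sub-heading in the same section. "If a dose is vomited within one hour of ingestion, it will be replaced", and "If vomiting occurs more than one hour after dosing, it will still be considered a complete dose". The time of the replacement is not given.

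Table 8 in Section 12.2.1 sets a weekly total for each dose level. The starting level is 60 mg twice weekly, 120 mg in all. Each reduced level can be given either as one Day 1 dose or split over Days 1 and 3. At level -2, for example, the choice is "80 mg selinexor/placebo on Day 1 OR 40 mg selinexor/placebo on Days 1 and 3".

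**The concern.** The missed-dose sentence assumes that a full week contains two doses. That is true of the starting schedule and of the split options, but not of the once-weekly options. The sentence does not exempt them, so two parts of the protocol give different totals for the same patient in the same week.

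A patient reaches a reduced level because of adverse events. At the two upper reduced levels the literal rule would put the week above the dose from which the patient was reduced. It also leaves unclear what the patient has been assigned. Section 13.3.2.1 defines an overdose by the dose assigned under the protocol and requires a report within 24 hours, so whether the second dose is reportable depends on which passage is taken to set the assignment.

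The vomited-dose text raises a smaller question: does a replaced dose count against the two-per-week cap and the 36-hour interval?

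**Working it through.** **Inputs.** Table 8 gives the dose levels, the schedules and the weekly totals. Section 12.2.4.1 gives the missed-dose rule, the cap of two doses per week, the 36-hour interval and the vomited-dose rule. Section 5.1 gives 12 doses per six-week cycle.

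**Reproducing the plan's figures.** Weekly total = sum of the scheduled doses. All nine schedules in Table 8 match their stated totals:
- Level 0: 60 + 60 = 120 mg.
- Level -1: 100, or 60 + 40 = 100 mg.
- Level -2: 80, or 40 + 40 = 80 mg.
- Level -3: 60, or 40 + 20 = 60 mg.
- Level -4: 40, or 20 + 20 = 40 mg.

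At two doses a week, 2 × 6 = 12 doses per cycle, as Section 5.1 states.

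**Missed dose, once-weekly option.** Literal weekly total = 2 × the assigned once-weekly dose. This assumes that each of the two doses is the size assigned, since the section says nothing about changing it.

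| Level | Table 8 total (mg) | Literal total (mg) | Against 120 mg starting total |
|---|---|---|---|
| -1 | 100 | 2 × 100 = 200 | 80 mg above |
| -2 | 80 | 2 × 80 = 160 | 40 mg above |
| -3 | 60 | 2 × 60 = 120 | equal |
| -4 | 40 | 2 × 40 = 80 | 40 mg below |

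The ratio to Table 8 is 2 at every level. Two doses do not exceed a cap of two, and two doses 36 hours apart fit in a 168-hour week, so neither limit stops it. For the split options, two doses in the week simply restore the Table 8 total. The milligram figures concern selinexor; Table 8 notes that placebo doses contain none.

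**Vomited dose, replaced once.**
- Two-dose schedule, vomited dose counted: 2 + 1 = 3 administrations, above the cap of 2. At level 0 the nominal amount is 180 mg against 120 mg.
- Two-dose schedule, vomited dose not counted: 2 doses, within the cap.
- Once-weekly schedule: 1 + 1 = 2 administrations, within the cap either way.
- Interval: a replacement given at once follows the vomited dose by about an hour or less, against 36 hours. If it is delayed, three administrations 36 hours apart span 2 × 36 = 72 hours of the 168, so the interval can be met.

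Whether a limit is broken therefore depends on two things the section leaves open: whether the vomited dose counts, and when the replacement is taken.

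**The case against.** The best defence is that the missed-dose sentence was plainly written for the standard twice-weekly schedule in Sections 12.1.3 and 12.1.4, that Table 8 states the weekly total for each level, and that patients are told to take treatment as prescribed. A sensible site would not double a reduced dose. In addition, every reduced level has a split option to which the problem does not apply. A dose withheld on the investigator's recommendation falls under the skipped-dose rule and is not made up, and Section 12.2.3 says that doses missed during infection are not replaced. The Pharmacy Manual, which Section 12.1.3 cites for administration details and which is not among the documents, may also settle the matter.

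Much of this stands, and it narrows how often the conflict would arise. It does not remove the conflict. The sentence carries no dose-level condition, the section does not define what separates a missed dose from a skipped one, and the result contradicts a figure stated in Table 8.

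On vomiting, the defence is stronger. The cap and the interval sit under the sub-heading for missed and delayed doses. The sentence on vomiting after one hour implies that a dose lost earlier is not complete, in which case its replacement would simply be the scheduled dose. That supports calling the point unclear and no more.

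**Conclusion.** The conflict between Section 12.2.4.1 and Table 8 is real but limited to patients on a once-weekly option at levels -1 to -4 who miss a dose within a week. Its size, if the rule is followed as written at the assigned dose, is a doubling of the weekly total: 200, 160, 120 or 80 mg instead of 100, 80, 60 or 40 mg. Two of the four results exceed the starting weekly total. The documents do not show how many patients this would affect. The vomited-dose text is an ambiguity.

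A reader might infer four stronger things that the documents do not support:
- *A wholly missed week is made up.* Section 12.2.4.1 says the reverse for a full week missed because of events unrelated to study treatment.
- *Replacing a vomited dose breaks the protocol's limits.* It does so only if the vomited dose counts or the replacement is immediate, and neither is stated.
- *An immediate replacement takes exposure past the 70 mg/m² ceiling.* The documents give no figure for absorption within the first hour. At the protocol's own conversion of 60 mg to about 35 mg/m², even two fully absorbed doses come to about 2 × 35 = 70 mg/m². Anything higher needs a small body surface area as well as near-complete absorption and immediate replacement.
- *The compliance threshold, and so the efficacy analysis, is materially affected.* One dose is 1 of 12 in a cycle on the twice-weekly schedule, and no effect on compliance has been quantified. The threshold governs only the supportive per-protocol population.

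Nor do the documents establish that the problem falls mainly on the patients least able to tolerate more drug, since many omissions for toxicity follow the skip or interruption rules.

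**What to change.** The sponsor should reconcile Section 12.2.4.1 with Table 8 so that the missed-dose text and the weekly totals agree for once-weekly schedules. The same clarification should make clear how a replaced vomited dose relates to the two-per-week cap and the 36-hour interval. Which passage should give way, and what the dosing instruction should be, is for the sponsor and its clinical advisers; nothing is proposed here. If the Pharmacy Manual already settles either point, it should be checked for consistency with the protocol.

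The cost is a short protocol clarification, about a sentence for each point, with the usual notice to sites. Sample size, alpha, event target and the primary analysis do not change.
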